# LIST OF ABBREVIATIONS

ASDAS	Ankylosing Spondylitic Disease Activity Score
ASDAS	Ankylosing Spondylitis Disease Activity Score Axial Spondyloarthritis
BILAG	British Isles Lupus Activity Group
BRAF-MDQ	Bristol Rheumatoid Arthritis Fatigue Multi-Dimensional Questionnaire
	•
CBA	Cognitive Behavioural Approach
CF	Chalder Fatigue Scale
CHaRT	Centre of Healthcare Randomised Trials
CI	Chief Investigator
CNORIS	Clinical Negligence and Other Risk Scheme
CONSORT	Consolidated Standards of Reporting Trials
CRF	Case Report Form
CRP	C-reactive protein
CTU	Clinical Trials Unit
DAS28	Disease Activity Score 28
DMC	Data Monitoring Committee
DTI	Diffusion Tensor Imaging
eGFR	Estimated glomerular filtration rate
ESR	Erythrocyte Sedimentation Rate
FA	Fractional Anisotropy
FSS	Fatigue Severity Scale
GCP	Good Clinical Practice
HADS	Hospital anxiety and depression scale
ICECAP	Investigating Choice Experiments for the preference of older people
	CAPability measures for adults
IRD	Inflammatory Rheumatic Disease
MAR	Missing at random
MRI	Magnetic Resonance Imaging
NHS	National Health Service
PA	Physical Activity
PASAT	Paced Auditory Serial Addition Test
PEP	Personalised Exercise Programme
PRoNTo	Pattern Recognition for Neuroimaging Toolbox
QALY	Quality Adjusted Life Years
QOL	Quality of Life
RA	Rheumatic Arthritis
RCT	Randomised Controlled Trial
REC	Research Ethics Committee
RPE	Rating of Perceived Exertion
SLE	Systemic Lupus Erythematosus
SOP	Standard Operating Procedure
S-VLA	Valued Life Activities short form
SWAT	Study Within A Trail
TDF	Theoretical Domains Framework
TSH	Thyroid Stimulating Hormone
VBM	Voxel-based morphometry
WPAI:SHP	Work Productivity and Activity Impairment Questionnaire: Specific Health
	Problem

# **SUMMARY**

Fatigue is pervasive, disabling and challenging to manage across all inflammatory rheumatic diseases (IRDs).

Primarily, we seek to advance the implementation of fatigue alleviating physical activity support programmes and cognitive-behavioural treatments within health services. We will individually test these interventions against usual care across multiple, rather than single, IRDs to enable improved patient access and resource utilisation. The interventions will be delivered centrally, by either telephone or internet-based audio/video calls such as Skype or Jabber, with a view to further enhancing cost-effectiveness.

The conduct of such a pragmatic study also presents a unique opportunity to a) investigate the underlying mechanisms of fatigue in order to optimise future interventions and b) identify the moderators of physical activity and cognitive-behavioural therapy efficacy so as to inform future stratified studies and patient triage pathways.

If successful, this study has the potential to unlock widespread access to much needed therapies and will provide vital insights into this commonly neglected patient priority.

# **1 INTRODUCTION**

# 1.1 Background

Despite major advances in the management of inflammatory rheumatic diseases (IRDs), patients remain burdened by their disease and cite fatigue as a principal problem. In rheumatoid arthritis (RA), for example, as many as 80% of patients report significant fatigue [1] and over 70% consider fatigue to be equal to pain in terms of burden [2]. Moreover, fatigue is a crucial determinant of impaired quality of life (QOL) [3,4] and a predictor of work disability [5,6]. Indeed, over 75% of patients identify fatigue as the main barrier to remaining in employment [7]. Studies in other IRDs, such as axial spondyloarthritis (AxSpA) and systemic lupus erythematosus (SLE), have reported similar fatigue prevalence of 66-85% [8,9] and have found the impact of fatigue on QOL and employment to be equally pronounced [10-12]. In spite of these profound consequences, patients feel this symptom is clinically ignored [13,14] and rheumatologists admit ignorance regarding its management [15].

This situation reflects the poor availability of suitable interventions within modern health care systems such as the NHS, but this is not to say that effective treatments do not exist. There is now considerable consensus across the health care community that non-pharmacological interventions, specifically cognitive behavioural approaches (CBA) and programmes designed to support increased physical activity, are valuable treatments which help IRD patients manage the functional challenges of their disease such as fatigue [16,17].

Our current team has made key contributions to the evidence base, which supports the use of these treatments for fatigue in IRDs [18-20].

However, current health care systems routinely contribute to substantial barriers to the implementation of these therapeutic options.

Firstly, existing studies – including our own – have only developed bespoke diseasespecific models of care, which vary in content, structure and method of delivery. Inevitably, this necessitates the development of multiple particular skill sets for the care providers if they are to equitably serve their diverse patient populations – a time consuming, costly and inefficient undertaking.

Secondly, patients find it challenging to commit to regular face-to-face treatment sessions (a common underpinning of existing CBA and exercise interventions). This is often due to a combination of health complications and the time-constrained nature of modern life, particularly relevant to those patients still in employment.

Thirdly, individual patients report substantial variation in their preference and response to the distinct interventions of CBA and physical activity [21,22].

# 1.2 Rationale for Study

It has becoming increasingly clear that:

a) similarities exist across chronic IRD disorders regarding the nature and likely mechanisms which maintain fatigue – such as dysfunctional activity behaviours [23-25] and illness beliefs [14,26,27], and so the application of standardised generic, rather than disease-specific, interventions may prove effective

b) alternative, more flexible, methods of remote delivery such as telephone and internetbased audio/video calls can be just as effective as traditional face to face interventions [28,29] and

c) in the future, the identification of baseline patient preferences and characteristics which can predict differential treatment effects (moderators) will be vital to inform a personalised triage approach to care [22,30].

Therefore, we propose a pragmatic trial, which will use pre-developed cognitive behavioural therapy and graded exercise therapy interventions, already considered the standard of care in heterogeneous primary fatigue populations. We have adapted them to a CBA and personalised exercise programme (PEP) so they may also be generically applicable across IRD-fatigue populations. We will now test whether these key non-pharmacological interventions can individually reduce fatigue, when delivered by the rheumatology team, across a mixture of IRDs using telephone or internet-based audio/video calls. In doing so, we will be able to explore potential moderating factors which may allow for the future triage of patients according to the most suitable intervention, but in addition investigate the precise mediators of the effect of treatment on IRD-related fatigue. The overall time scale of the LIFT study is summarised in a GANTT chart (Figure 1).

#### Lessening the Impact of Fatigue in IRD

	2016													2018							2019									2020																		
	Jul	Jul         Aug         Sep         Oct         Nov         Dec           1         2         3         4         5					Jan	Feb	Mar	Apr	May	Jun	Jul	Aug	Sep	Oct	Nov	Dec	Jan	Feb	Mar	Apr	May	Jun	Jul	Aug	Sep (	Oct N	Nov D	lec J	lan F	eb M	ar Ap	r May	/ Jun	Jul	Aug	Sep	Oct	Nov	Dec	Jan	Feb	Mar A	Apr M	√ay J	Jun Jul	
Month		1	2	3	4	5	6	7	8	9	10	11	12	13	14	15	16	17	18	19	20	21	22	23	24	25	26	27	28 2	29 3	30	31 3	2 33	34	35	36	37	38	39	40	41	42	43	44 4	45 4	46	47 48	3
Funding (LIFT)																																																
Protocol development																																																
Intervention development																																																
Feedback on intervention documents																																																
Preparation of study documents (PIS)																																																
Establish oversight committees (DMC, TSC, TMG)																																																
Approvals LIFT (Sponsor, REC, R&D)																																																
Approvals LIFT MRI sub-study (Sponsor, REC, R&D)																																																
Study database																																																
Site initiation process and training																																																
Therapist training for intervention (CBA/PEP)																																																
Recruitment phase (LIFT))																																																
Intervention																																																
Study assessment visits																																																
																																																_
Recruitment phase (MRI sub-study)																																																
Optional: MRI scan #1 (pre-intervention)																																																
Optional: MRI scan #2 (post-intervention)																																																_
																																																_
Recruitment phase (Qualitative Evaluation sub-study)																															_																	_
Qualitative Evaluation interviews (participants)																																																_
Qualitative Evaluation interviews (therapists)																																																_
																																														$\rightarrow$		_
																																																_
Data entry																																																_
Data analysis and statistic																																																_
Data processing, analysis and report LIFT MRI sub-study																																																_
																																	_															_
Publications																																														$\rightarrow$		_
protocol																																														$\square$		
study main outcomes																																																_
health economic analysis																																																
qualitative evaluation																			1																	1												

Figure 1. GANTT chart of LIFT study, LIFT MRI sub-study and qualitative evaluation sub-study

# 2 STUDY OBJECTIVES

# 2.1 Primary Objective

Primarily, we seek to test our hypothesis that usual care in addition to either standardised CBA or PEP interventions is more effective than usual care alone to lessen the impact and severity of fatigue after 56 weeks.

# 2.2 Secondary Objectives

We will also explore the underlying moderators (in order to inform future patient triage) and mediators (in order to optimise future interventions) of IRD related fatigue.

# 3 OUTCOMES

All outcome and mediator data will be assessed at randomisation (baseline) and then, on average, 10 weeks, 28 weeks and 56 weeks thereafter (by questionnaire unless stated) in all participants. The outcome measures at each time point and their source (i.e. questionnaire, medical record, blood sample, diary) are summarised in the study matrix (see 3.8).

# 3.1 **Primary Outcome**

The primary outcome fatigue is determined with the Chalder Fatigue Scale (CF) [31] using the Likert scoring, assessing the physical and mental symptoms of fatigue, and the Fatigue Severity Scale (FSS) [32] assessing the impact of fatigue after 56 weeks. If the effect of intervention is positive on the CF, then the FSS outcome will be formally analysed. Should the intervention have no effect on the CF, then an explorative analysis of the FSS outcome will be performed (details see 10.2).

# 3.2 Secondary Outcomes

The secondary outcomes are:

- *Fatigue:* Bristol Rheumatoid Arthritis Fatigue Multi-Dimensional Questionnaire [33] (BRAF-MDQ) assessing physical, living, cognition and emotional aspects of fatigue
- *Quality of life & health utility index:* Short Form-12 [34] assessing functional health and wellbeing from the patient's perspective
- Pain: Pain numerical rating scale [35] assessing pain intensity
- Anxiety and depression: Hospital anxiety and depression scale (HADS) [36]
- *Sleep:* Sleep problem scale [37]
- *Impact on work:* Work Productivity and Activity Impairment Questionnaire: Specific Health Problem (WPAI:SHP) [38]
- Impact on activities: Valued Life Activities Scale (short form S-VLA) [39]
- Global outcome: change of global health

# 3.3 Mediator/moderator data

While many outcome measures may also function as mediators, or their baseline values as moderators, more detailed cognitive, behavioural, clinical and physical data will be important in order to fully characterise these factors.

*Cognitions and behaviours:* Brief Illness Perception Questionnaire [40], Behavioural Response to Illness Questionnaire [41]

*Clinical:* Presence of fibromyalgia [42], serological status, erosive status, disease duration, previous and current pharmacological therapies, disease activity: self-reported, DAS28 for RA (mandatory), other disease specific activity measures (non-mandatory), inflammation (CRP/ESR), presence of other co-morbidities (Charlson Comorbidity Index).

*Physical:* Physical activity profiles measured by an activity monitor (*activ*PAL, Paltechnologies Ltd, Glasgow). The *activ*PAL will be fitted to the participant at each assessment session and participants instructed to remove the device and post it back to the research team after seven days in the stamped addressed envelope provided to them.

*Quantifying aerobic fitness:* we will employ a step test, which involves participants wearing a heart rate monitor and stepping onto a 10 inch high box for three minutes at different stepping rates (stage 1:17, stage 2:26 and stage 3: 34 steps per minute – guided by a metronome). Participants stop the test if the heart reaches 65% of predicted maximal heart rate (220-age or 190-age if participant is prescribed beta-blocker) at the end of any stage. In addition, values of Borg Rating of Perceived Exertion (RPE) are collected. One minute of rest is given between stages and maximal oxygen uptake is estimated from heart rate recordings according to established equations [43].

*Neuroimaging data:* Participants will have an option to undertake a multi-modal magnetic resonance imaging (MRI) brain scan (see Appendix 2)

# 3.4 Quantitative process evaluation

#### 3.4.1 Patient preference

Participants will be given short synopsis of all three treatments, usual care, CBA and PEP interventions as treatment for IRD-related fatigue. They will then be asked about which treatment they would choose if they had a choice, as well as about their strength of preference.

# 3.4.2 Patient adherence and acceptability

Patient adherence to the interventions will be monitored via attendance records kept by the therapists. In addition, participants receiving the CBA or PEP interventions will be contacted by telephone interview by member of trial office Aberdeen at time of session 4 (approximately week 8) and session 8 (approximately week 26). They will be asked to indicate on a scale from 0 (not at all) to 10 (completely), if they think that this treatment is the right approach and their willingness to engage and adhere to the intervention. At the same time, the therapists will be asked during supervision to what extent they think that the participant has engaged with treatment and adhered to the agreed actions and

plans. Intervention acceptance by participants will be evaluated in all three treatment arms using the Client Satisfaction Questionnaire [44] at 28 weeks.

# 3.5 Qualitative process evaluation

We will conduct qualitative evaluations of both participants who received CBA or PEP and rheumatology health care professionals who will deliver the interventions (see Appendix 3).

# 3.6 Economic evaluation

An economic evaluation will be conducted from both a health care system and societal perspective. Participants will be asked to record in a diary all types and duration of hospital admissions, frequency of visits to hospital for outpatient attendances, and other visits to or from relevant health professionals (e.g. general practitioners, nurse practitioners, physiotherapists) and specify whether the main reason for the visit was fatigue. The participant will be asked to keep the diaries between the baseline and third assessment visit (approximately 28 weeks). Furthermore they will be asked to keep diaries for two weeks after the third assessment visit and two weeks before they return for the last assessment visit. National sources of unit cost data will be applied to value resource use (HRG Reference Costs, Unit Costs of Health and Social Care). The costs associated with delivery of the interventions will be estimated using records kept by therapists of the number and duration of calls per patient.

Patients will be asked to report any contacts with private practitioners, and the costs of over the counter medication/complementary therapies purchased. This also includes additional expenses related to their condition or fatigue as well as if there was an impact on paid and unpaid work.

Health-related quality of life data will be collected using the SF-12 and these data will be converted to quality of life weights using published tariffs. These data will then be used to calculate Quality Adjusted Life Years (QALYs). As the intervention may affect general well-being as well as reduce fatigue, we will also collect values for changes in well-being data using the ICECAP instrument [45] and changes in life satisfaction [46].

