Patient adherence (attendance records)	SR			х	х	Х					
Patient engagement and adherence (telephone call)	Q	3			х	Х					
Patent engagement and adherence (therapist view)	Q	2			х	Х					
Patient acceptability (Client Satisfaction Questionnaire)	Q	8				~					
Qualitative process evaluation											
Qualitative evaluation in participants (5% sample)	I										
Qualitative evaluation in therapists (all)	I										
Economic evaluation											
Health care costs from participants per diaries	D			✓	✓	√	✓				
Additional (personal) costs for participant per diaries	D			✓	✓	√	✓				
Cost associated with delivery of therapy	SR			✓	✓	√	✓				
Health related quality of life using SF-12 for calculation of QALY				✓	✓	√	✓				
Changes in well-being data using ICECAP	Q	5		✓	✓	√	✓				
Changes in life satisfaction	Q	1		~	✓	~	✓				
Optional blood sample for future ethically approved researc	 h										
1 x PAXgene RNA				✓	✓	√					
1 x PAXgene DNA				✓							
1 x serum				✓	✓	√					

**Key: B**, blood sample taken specifically for LIFT; **CRF**, part of case report form completed by research nurse during visit; **D**, separate diary for participant to keep; **I**, interviews performed after the last follow-up visit; **MR**, information extracted from medical record; **Q**, data derived from questionnaire; **S**, information obtained during pre-study invite; **SC**, Scanner; **SR**, information extracted from LIFT study records and logs; **T**, test done specifically for LIFT; **x**, outcome collection at same time frame but separate from assessment visit

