# 4.3.1 Description of interventions

*Usual care:* Due to issues of treatment access, patient education using Arthritis Research UK's information booklet for self-management of fatigue [49] represents usual care in almost all UK rheumatology centres and is freely available. The leaflet covers the major relevant topics (including fatigue validation, energy management, priorities, sleep, stress, and assertiveness) underpinned by goal-setting and self-monitoring of activity. It encourages, at several key points that the patient asks their rheumatology team for support to work through the booklet. We will not restrict what usual care may involve, but will monitor the care received for all participants as part of our health economics analysis (see 3.6).

The *Cognitive behavioural approach (CBA)* is a structured psychological intervention, which explicitly aims to replace unhelpful beliefs and behaviours with more adaptive ones. In this study, the CBA will target a number of unhelpful behavioural patterns such as 'activity avoidance' and 'all or nothing'. These can lead to negative mood states, which enhance the perception of fatigue even further. Following a brief assessment of individual patients beliefs and behaviours surrounding fatigue, the aim of the treatment is to change unhelpful beliefs and behavioural factors through the application of patient-centred strategies and behavioural activities, which are supported by written materials and regular consultations with rheumatology health care professionals. The participants will receive additional key leaflets and diaries to assist them with making changes to manage fatigue. The times and duration of keeping the diary as well as the exchange of content will be set individually for each patient following assessment and in collaboration with the allocated therapist. For example the participant may be asked to keep the rest and activity dairy for up to two weeks before a session with the therapist and they will talk about it via video call where the participant shows the diary to the therapist.

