# 7 STUDY AND SAFETY ASSESSMENTS

There are unlikely to be major safety issues with our proposed non-pharmacological interventions. However, if the rheumatology healthcare professional delivering CBA and PEP or any study personnel have any safety concerns, we will follow a specific Standard Operating Procedure (SOP) for adverse events in non-CTIMP studies. In brief, they will use a standard template after secure log-in into the study database. A designated investigator with rheumatology background and/or designated experienced investigators responsible for the training of therapists as summarised in the delegation log in the TMF will then assess and categorise events according to the SOP to determine if the event is expected, related and/or serious. There will be access to independent clinicians (both rheumatology and psychology), if required. We will make every effort to report all confirmed related serious adverse events to the sponsor within 24 working hours after the CI has been made aware of them.

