# 8 DATA COLLECTION AND MANAGEMENT

# 8.1 Data Collection

Case Report Forms (CRF), including medical outcomes, and guestionnaires as indicated under 3 and 3.8, respectively, are completed during the assessment visits at the local study site either on paper or online in the database. All participants will have the option to complete the questionnaires and diaries online in the database (requires a valid email address) or on paper depending on personal preference. There will be the option to complete the questionnaire at home, if the participant requests this. Paper questionnaires will then be returned via pre-paid envelopes to the study centre. If the participant opted for online entry, he/she will receive secure access limited to own data in the database via a link sent to a provided email address and/or log-in code. Paper health economic diaries which are filled by the participant throughout the study will also be returned either in person to the local study site or by pre-paid envelope to the study centre Aberdeen. If a participant is entirely unable (e.g. due to mobility issues) to attend a follow-up visit at 10, 28 or 56 weeks in person, but is still happy to continue with the follow-up, the data collection (except blood samples, step test, DAS28) will be done by phone and post. The option for remote data collection will only be used in selected cases at the discretion of the PI/CI/Co-CI if an assessment visit at the local site would be delayed for at least 3 weeks. In case of a participant unable to attend a follow-up visit, the paper questionnaire, diaries and ActivPAL will be sent out by post and will be returned via pre-paid envelopes to either the study centre or the local study site. In case of a local site unable to perform a follow-up visit, the Trial Office staff will perform the remote visit instead. Information from medical records will be taken retrospectively once the local site is in a position again to continue. Any participants who do not return a questionnaire at the 56 weeks follow-up visit will be telephoned and asked some questions over the phone about fatigue (i.e. Chalder Fatigue Scale, Fatigue Severity Scale), Patient Global Impression of Change, Disease activity and intensity of pain. Personal data, including postal address, phone numbers (landline and mobile), email addresses, and anonymised data files for study outcomes are stored in locked filing cabinets (hard copy) and in a bespoke database provided and maintained by CHaRT (see 8.2) as well as secured shared drives with access via password controlled computers (university and NHS networks) by study staff only (electronic data) (see also 13.1.1 and 13.1.2). Participants will have the option to undertake a multi-modal MRI brain scan (see Appendix 2). A subgroup of participants and all therapists will have the option to take part in an interview as part of the Qualitative Evaluation sub-study (see Appendix 3).

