Quantitative evaluation					
Patient preference	~	/			
Patient adherence (attendance records)	>	(x	x	
Patient engagement and adherence (telephone)			х	x	
Patient engagement and adherence (therapist view)			x	x	
Patient acceptability (Client Satisfaction				✓	
Questionnaire)					

S -Secondary analyses phase \$ PA summarised data to be threaded for the secondary analyses phase

D – derived variables

SAP ver

* For monitoring purpose only during the course of the trial - not in final analysis

the number of participants Lost to Follow-up (LTF) and/or who Discontinued the intervention will also be monitored along with reasonsrHCPs: rheumatology health care professionalsCBA: Cognitive Behavioural ApproachPEP: Personalised Exercise Programme

8 Trial Population

Patients with rheumatologist diagnosed IRDs (e.g. Rheumatoid Arthritis [RA], Systemic Lupus Erythematosus [SLE] and AxSpA, psoriatic arthritis, vasculitis or Sjogren's Syndrome).

9 Adverse events:

An adverse event (AE) is defined as any untoward medical occurrence in a participant, not necessarily being intervention related. Adverse events are collated according to the protocol (defined by the appropriate SOP). An adverse event is defined as "serious" (SAE) if it

- results in death
- is life threatening
- requires or prolongs inpatient hospitalisation
- results in persistent/significant disability/incapacity
- is otherwise considered medically significant by the investigator.

There are no related serious AEs expected in this trial. However, any serious related AEs that do occur will be recorded following specific Standard Operating Procedure (SOP) for adverse events in non-CTIMP studies. Hospitalisations for elective treatment of a pre-existing condition are not considered as an AE or SAE. Complications occurring during such hospitalisation are also not AEs or SAEs.

10 Sample Size and Power Calculation

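### Hospital admissions recorded in participant diaries have no stated route to SAE review, so Table 6 may under-count SAEs, and unequally by arm

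*Protocol*

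**What the plan says.** **Diary content and use.** Protocol 3.6 states: "Participants will be asked to record in a diary all types and duration of hospital admissions". Protocol 4.3.1 says the trial "will monitor the care received for all participants as part of our health economics analysis", which fixes both the coverage (all arms) and the stated purpose. In the study matrix (Protocol 3.8) the row "Health care costs from participants per diaries" stands under economic evaluation and nowhere else.

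**Diary period.** Protocol 3.6 has diaries kept from baseline to the third visit at about 28 weeks. After that, participants are to "keep diaries for two weeks after the third assessment visit and two weeks before they return for the last assessment visit". Protocol 8.1 reads differently: "Paper health economic diaries which are filled by the participant throughout the study".

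**Safety route.** Under Protocol 7, an event enters when the treating professional or any other study personnel has a safety concern; then "they will use a standard template after secure log-in into the study database". A designated investigator classifies it under an SOP that is not among the documents. The diary is not named as a source.

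**Definitions and table.** SAP 9 lists as serious an event that "requires or prolongs inpatient hospitalisation". It defines an adverse event without regard to relatedness, and exempts elective admissions for a pre-existing condition and complications arising during them. Its explicit recording commitment, however, covers only serious events that are related. SAP 13.2, Table 6, is headed simply as serious adverse events, by arm, with no data source stated.

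**The concern.** The trial asks every participant, in the same way in each arm, about the commonest kind of event that can meet a seriousness criterion. As written, the answers go only to the cost analysis. The safety table rests instead on what staff happen to learn and choose to report.

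That route is not even across arms. A participant in CBA or PEP speaks to a therapist repeatedly and is telephoned by the trial office; a usual-care participant sees trial staff only at assessment visits. If admissions come to light mainly through contact, the active arms will show more of their events than the control arm, and all arms may show too few. The direction could make the interventions look less safe than they are. The overall shortfall could make the trial look safer than it is. The same data feed the monitoring committee, which SAP 4 asks to look specifically at safety.

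A second problem sits alongside. For the 24 weeks without a diary under Protocol 3.6, no scheduled question about admissions is stated in any arm.

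**Working it through.** **1. Denominator.** The plan's own figure is reproduced first. Inputs from Protocol 10.1: difference 2, SD 4, 2.5% per comparison, power 90%; two-sided from SAP 11.1.

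n per arm = 2 × (2.2414 + 1.2816)² × (4/2)² = 2 × 12.41 × 4 = 99.3, rounded up to 100. With 20% dropout (Protocol 5.1): 100 / 0.80 = 125 per arm; 3 × 125 = 375. The plan's figures hold.

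**2. Diary coverage under Protocol 3.6.**

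| Window | Weeks | Length |
|---|---|---|
| Baseline to third visit | 0–28 | 28 |
| After third visit | 28–30 | 2 |
| Before last visit | 54–56 | 2 |
| Covered | | 32 of 56 = 57.1% |
| Not covered | 30–54 | 24 of 56 = 42.9% |

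With 375 participants and no loss: 375 × 24 = 9,000 of 375 × 56 = 21,000 person-weeks have no diary.

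**3. Scheduled trial contacts beyond the assessment visits.** Inputs from Protocol 4.1, 4.3.2 and 3.4.2.

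| | CBA or PEP | Usual care |
|---|---|---|
| Treatment sessions | 7 | 0 |
| Booster | 1 | 0 |
| Trial-office calls (sessions 4 and 8) | 2 | 0 |
| Total | 10 | 0 |
| Follow-up visits (10, 28, 56 weeks) | 3 | 3 |

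So there are 13 scheduled post-baseline contacts against 3. The latest booster is at week 8 + 22 = 30, so on schedule the extra contacts fall inside the main diary period. The diary is therefore available exactly where contact differs most.

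**4. Illustration of size.** The documents give no admission rate. The rates below are assumptions, taken as constant and non-elective, with 375 participants, no loss and full diary return. Person-years: 375 × 32/52 = 230.8 covered, 375 × 24/52 = 173.1 not covered, 403.8 in all.

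| Assumed rate per person-year | Diary weeks | Weeks 30–54 | Total |
|---|---|---|---|
| 0.05 | 11.5 | 8.7 | 20.2 |
| 0.10 | 23.1 | 17.3 | 40.4 |
| 0.20 | 46.2 | 34.6 | 80.8 |

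These are admissions that would need review, not counts of missed SAEs. Planned dropout and unreturned diaries would lower the diary column.

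**5. Scope of Table 6.** Three parts of the SAP do not fit together: an all-cause definition of an adverse event, a recording commitment limited to related serious events, and a table with an unqualified heading, a usual-care column and a row for deaths. The first and third suggest all SAEs; the second suggests related ones only.

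**The case against.** The strongest reply is that unrelated admissions may lie outside Table 6 by design. SAP 9 commits to recording related serious events, and Protocol 7 puts only those on the 24-hour report to the sponsor. A reader might infer that the trial will publish two contradictory counts of the same events. The documents do not support that: an admissions count for costing and a count of related SAEs measure different things. What stands is that the scope is not settled.

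A reader might also infer that every diary admission is an SAE the trial already holds. It is not. The diary asks for type and duration and names no diagnosis, and SAP 9 exempts elective admissions and their complications. An entry is a prompt for review. It also exists only within the diary windows.

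Nor is it right that weeks 30 to 54 have no capture at all. Any study personnel may report a concern, and all arms have a 56-week visit. What is missing is a scheduled question. A late booster does not sharpen this point, since week 30 is the edge of the diary window and not inside the gap. If Protocol 8.1 is the correct description, the gap closes, but the missing link to safety review remains.

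Finally, the SOP is not among the documents and may already contain such a check. The claim is therefore that no route is stated in the protocol or SAP, not that none exists.

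**Conclusion.** The point holds in this form. Within the diary windows of Protocol 3.6 (32 of 56 weeks), admissions are collected alike in all arms but have no stated path to SAE review. The stated path depends on staff awareness, with 13 scheduled post-baseline contacts in the active arms against 3 in usual care, so under-ascertainment that differs by arm is a real possibility. For the other 24 weeks neither a diary nor a scheduled admission question is stated, subject to the conflict between Protocol 3.6 and 8.1. The scope of Table 6 is a separate inconsistency that must be resolved before its counts can be interpreted.

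The coverage and contact figures follow from the documents. The admission counts do not: they rest on assumed rates and are illustrative only. The point affects safety reporting and monitoring; it does not touch the primary efficacy analysis. It should be put right, but does not threaten the trial's main conclusion.

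**What to change.** 1. **Protocol 7 and SAP 9.** State that each diary-reported admission is checked against the adverse event log when the diary is entered. Unmatched admissions go to the designated investigator, who classifies seriousness and relatedness under the SOP and applies both SAP 9 exemptions. They should not be entered as SAEs automatically. If the SOP already requires this, say so.
2. **Week 56, all arms.** At the existing notes and CRF review, record the date and reason of any admission in the period without diaries. Access to hospital notes is already an inclusion criterion (Protocol 5.2.3), and the study matrix already draws on notes at follow-up visits.
3. **SAP 13.2.** State that Table 6 is produced after this reconciliation, and whether it shows all SAEs or related SAEs only. Align SAP 9 with the answer.
4. **Protocol 3.6 and 8.1.** Reconcile the two descriptions of the diary period.

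The cost is some data-management and extraction time, and possibly a higher reported SAE count. No additional visit or procedure is needed.
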